**DATE: February 10, 2023**

# 1. Research Background

Renal cell carcinoma(RCC) is a common tumor of the urinary system, accounting for 4.1% of all malignant tumors. 1 According to the latest GLOBOCAN data, in 2021, there are 71,676 new cases and 15,259 deaths of kidney cancer in the United States and 77,410 new cases and 46,345 deaths in China. The incidence of kidney cancer in China has increased at an average annual rate of 6.5% over the past 20 years and has surpassed bladder cancer in the number of deaths related to urological tumors, ranking first. Since renal ultrasound is a routine medical examination for people over 40 years old in China, most of the patients are in the early stage of limited renal cancer when they are diagnosed.

In the current guidelines, nephron sparing surgery(NSS) is the preferred treatment for early-stage limited kidney cancer. NSS includes partial nephrectomy(PN) and tumor enucleation(TE). Unlike PN, TE is a surgical procedure that bluntly separates the tumor along the natural cutting plane between the pseudocapsule and healthy parenchyma, completely removing the tumor tissue while maximizing the preservation of normal kidney tissue. However, most surgeons currently perform partial nephrectomy. The reason for this phenomenon is first, the problem of concept. most surgeons doubt whether TE can clean up tumor tissue. on the other hand, enucleation requires surgeons to have a better understanding of the anatomical relationship around the tumor and accurately separate the tumor envelope and normal kidney tissue, and its surgical difficulty is higher than that of traditional PN.

Our team has conducted a clinical meta-analysis on these two procedures, and the results showed that TE has the advantages of less trauma, faster postoperative recovery, and better protection of renal function than PN, without increasing the risk of tumor recurrence.

Minervini et al. analyzed the pseudocapsule integrity of 304 specimens after TE, founding that 51% of the specimens had an intact pseudocapsule and 49% had infiltrating tumor cells on the pseudocapsule. but all specimens had negative cut margins and there is no statistical difference in 5-year progression-free survival. thus they concluded that enucleation for renal cancer is a safe surgical procedure. In the past 10 years, our team has performed more than 500 kidney cancer enucleations without any positive margins and no patient has experienced in local recurrence. In addition, traditional PN requires temporary blockage of the renal artery to achieve a relatively bloodless operating environment to ensure the safety of tumor removal. But prolonged warm ischemia is bound to affect the function of normal kidney tissue. Therefore reducing thermal ischemia time up to zero ischemia time has become a quest for surgeons. The combination of zero-ischemia technique on the basis of kidney cancer enucleation is a field that has rarely been touched.

Therefore reducing thermal ischemia time up to zero ischemia time has become a quest for surgeons. Clinically, the combination of zero-ischemia technique on the basis of kidney cancer enucleation is a field that has rarely been touched. In the last 3 years, our team has performed nearly 100 cases of zero-ischemic renal tumor enucleation, and this procedure can maximize the protection of renal parenchyma and renal function under the premise of ensuring tumor safety. In conclusion, if zero ischemia enucleation can be applied and popularized to limited renal cancer surgery, it will benefit a large number of patients and improve the prognosis.

## **2. Research objectives**

Main objective: the efficacy (rate of change in renal function GFR, overall survival OS, tumor-free survival TFS, progression-free survival PFS, etc.) and safety (positive incision margin rate, intraoperative blood loss, postoperative complication rate, etc.) of unassisted zero-ischemia enucleation in the surgical treatment of patients with early stage (T1) renal cancer.

Secondary objectives: differences between unassisted zero ischemic enucleation of renal cancer and partial nephrectomy with clamping of the hilum in the surgical management of patients with renal cancer and the role of the modified ABC score in the assessment of renal cancer.

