## **3. Study content and design**

This study aims to evaluate the effectiveness and safety of the surgery by using renal cancer patients who met the inclusion criteria. Summarizing the preoperative, perioperative, and postoperative data, and evaluating the operative time, intraoperative bleeding, postoperative hospitalization days, postoperative complication rate, postoperative short-term, intermediate, and long-term renal function indexes, overall survival, tumor-free survival, progression-free survival and postoperative renal cancer recurrence rate of the patients.

Statistical software is used to describe the characteristics of patient data. T-test, rank sum test, multi-factor regression, and cox regression are used to investigate the effects of each factor on the treatment outcome and prognosis of patients undergoing zero-ischemic renal enucleation, to describe whether there are differences in the safety and efficacy of zero ischemic renal enucleation compared with traditional

partial nephrectomy for the treatment of stage T1 renal carcinoma.

This study used a retrospective research trial design to include 73 patients who underwent zero-ischemic enucleation and 73 patients who underwent traditional partial nephrectomy from 2014 to 2022, for a total of 146 patients. The formula for calculating the sample size is as follows.

$$n = [z_{\alpha}\sqrt{2\bar{p}\bar{q}} + z_{\beta}\sqrt{p_0q_0 + p_1q_1}]^2 p / (p_1 - p_0)^2$$

Figure 1. Estimated sample size calculation

note:  $Z_{\alpha}$ 、 $Z_{\beta}$  are the quartiles under standard normal distribution.

$p_1$ : Expected morbidity in the exposed group.

$p_0$ : Expected incidence in the control group.

$q_1$ :  $q_1 = 1 - p_1$ .

$q_0$ :  $q_0 = 1 - p_0$ .

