## **5. Experimental program**

**5.1** The patients are screened according to the inclusion and exclusion criteria. Then the patients are divided into two groups according to whether they underwent zero-ischemic enucleation or partial nephrectomy, with the zero-ischemic enucleation group as the test group and the partial nephrectomy group as the control group. Describing the preoperative conditions (age, sex, Anatomy of tumor, RENAL score, ABC score, preoperative renal function), the perioperative conditions (operation time, intraoperative bleeding, perioperative complications, negative/positive specimen margins, postoperative renal function changes, postoperative hospitalization days), and the postoperative condition (follow-up renal function, tumor recurrence rate, overall survival, tumor-free survival, progression-free survival).

**5.2** The data of the two groups are corrected for baseline and screened so that there is no statistical difference in the number of patients, gender age, tumor anatomy, renal function and other preoperative conditions between the two groups (t-test/rank sum test  $p > 0.05$ ).

**5.3** The zero ischemic renal enucleation group is grouped according to RENAL score, ABC score and other scoring criteria. Different preoperative tumor score groupings are used as exposure

factors, and the percentage decrease of postoperative renal function compared with preoperative, perioperative complication rate and postoperative survival rate are used as outcome variables to analyze the association between exposure factors and outcome, to investigate the association of different factors on the surgical outcome of zero ischemic renal enucleation.

**5.4** Using zero-ischemic nephrectomy or partial nephrectomy with clamping of the renal hilum as the exposure factor. T-test/rank sum test and one-way regression are used to compare the efficacy indexes such as negative/positive tumor margins, postoperative and follow-up renal function, survival rate, and safety indexes such as perioperative complication rate and intraoperative bleeding between the two groups to investigate whether there is a statistical difference in their treatment safety and efficacy. Then we investigated whether there are statistical differences and correlations between the safety and efficacy of the treatment, and whether there are statistical differences in survival outcomes between the two groups by multifactorial cox regression.

[figure not shown]

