### **6.3 Statistics**

Data entry: Enter the age, gender, kidney cancer stage and prognosis follow-up of the subjects.

Data management: The data are presented by number, and all personnel except the initial data entry personnel do not have access to the subjects' initial information (including subjects' personal information such as subjects' names, addresses, occupations and other sensitive information). There is no direct contact between the data entry personnel and the subjects, and all privacy of the subjects is protected from disclosure.

All hypothesis tests are two-sided, and differences are considered statistically significant at  $P < 0.05$ . Baseline data are evaluated for comparability between groups, and two-tailed statistical tests are performed at the  $\alpha=5\%$  level. The chi-square test or Fisher's exact probability method is used for comparison between groups for count data, the t-test for comparison between groups for measurement data, and the rank sum test for comparison between groups for nonparametric variables.

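### No primary outcome or time point is named, section 2 does not match the two-group design, and every two-sided P < 0.05 counts as significant with no hierarchy or adjustment

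*Combined protocol and SAP*

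**What the plan says.** - **Section 2, main objective.** It reads "Main objective: the efficacy (rate of change in renal function GFR, overall survival OS, tumor-free survival TFS, progression-free survival PFS, etc.) and safety". Four efficacy outcomes are named (change in GFR, OS, TFS, PFS), then three safety outcomes (positive margins, blood loss, complications). Both lists end in 'etc.', and the sentence names no comparator.
- **Section 2, secondary objectives.** These are the "differences between unassisted zero ischemic enucleation of renal cancer and partial nephrectomy with clamping of the hilum", with no outcome attached, and the role of the modified ABC score.
- **Section 3.** The design has two groups of 73, and the sample-size formula is for two proportions. The plan is for "evaluating the operative time, intraoperative bleeding, postoperative hospitalization days, postoperative complication rate, postoperative short-term, intermediate, and long-term renal function indexes", followed by survival outcomes and recurrence. The three renal-function periods have no dates.
- **Section 5.3.** Within the enucleation group, RENAL, ABC and other score groupings are related to renal-function decline, complications and survival.
- **Section 5.4.** Between groups, tests are "used to compare the efficacy indexes such as negative/positive tumor margins, postoperative and follow-up renal function, survival rate, and safety indexes" such as complications and bleeding. Survival is then examined again, to see "whether there are statistical differences in survival outcomes between the two groups by multifactorial cox regression".
- **Section 6.3.** "All hypothesis tests are two-sided, and differences are considered statistically significant at" P < 0.05. No section gives a primary outcome, a testing order, a split of alpha or an adjustment.

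**The concern.** A reader of the results could not tell which one answers the study question. Section 2 makes the description of enucleation the main aim, while sections 3 and 5.4 make the comparison the substance of the work. The list of compared outcomes is open, and renal function can be tested at several undated times. Under the rule in section 6.3, a chance P < 0.05 on any outcome at any period counts as a difference in efficacy or safety, with the same standing as any other result.

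The error can also run the other way. Without a stated main question, a non-significant margin or survival result may be taken to show that the operations do not differ, which a non-significant test cannot show.

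The timing adds to this. The plan is dated February 2023, the operations took place from 2014 to 2022, and section 7 says that previous case information is used. With records already in existence, an unranked and open list leaves room for selective emphasis, even if none is intended.

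**Working it through.** **1. Does the sample size identify a primary outcome?** No. Section 3 gives 73 per group and a two-proportion formula, but no event, no values for the two proportions and no power. The 73 therefore cannot be reproduced, and many inputs fit it. Assuming two-sided 0.05, 80% power and no continuity correction, 40% versus 19% and 40% versus 63% both give 73.

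**2. How many tests are planned?** The documents do not fix this.
- Section 5.4 names five kinds of between-group outcome: margins, renal function, survival, complications and bleeding. The list is open.
- Section 3 allows three renal-function periods, and adds operative time, hospital days and recurrence.
- Section 5.3 gives at least 2 scores × 3 outcomes = 6 pairings if each named score is set against each outcome, before any 'other' score.

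**3. Illustration for the between-group comparison.** Inputs: alpha 0.05 two-sided per test (section 6.3) and no true difference on any outcome. The choice of tests and the correlations are assumptions. Test statistics are treated as normal, with significance at |z| > 1.96.

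*Three tests: GFR change at one time, blood loss, complications.*
- Independent: 1 − 0.95³ = 14.3%.
- Equal correlation 0.5: 12.5%. Equal correlation 0.8: 9.8%. Both are from the equicorrelated normal distribution.

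*GFR at three correlated periods, with blood loss and complications independent of GFR and of each other.* The chance of at least one false positive is 1 − (1 − F) × 0.95², where F is the chance that at least one of the three GFR tests is falsely significant.

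| Correlation between GFR periods | F | At least one false positive, all five tests |
|---|---|---|
| 0.5 | 12.5% | 1 − 0.875 × 0.9025 = 21.1% |
| 0.7 | 10.9% | 1 − 0.891 × 0.9025 = 19.6% |
| 0.9 | 8.4% | 1 − 0.916 × 0.9025 = 17.3% |

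**4. Why margins are left out of the count.** Section 1 reports "more than 500 kidney cancer enucleations without any positive margins", so few positive margins are likely in the enucleation group. Section 6.3 allows Fisher's exact test, which is conservative with sparse data. At 73 per group its true two-sided error is 0.17% if both groups have 2% positive margins, and 2.6% at 10% (assumed rates). Such tests add little to the false-positive risk.

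**5. Sensitivity.** If complications are tested by Fisher's test at an assumed 10% rate, their error is 2.6% rather than 5%. Three independent tests then give 1 − 0.95² × 0.974 = 12.1% instead of 14.3%. The chi-square test, which section 6.3 also allows, would be nearer the full 5%.

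The score-group tests in section 5.3 are not included in these figures and would add to them.

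**The case against.** The strongest reply is that this is a retrospective record review with modest aims. Section 3 speaks of describing whether there are differences and section 5.4 of investigating them; no superiority or equivalence claim is planned. In such a study a formal hierarchy is partly a matter of preference, and labelling the results exploratory would do. This largely stands, and it shapes the fix. But the plan never calls its results exploratory, and section 6.3 applies one significance rule to all of them.

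A second reply is that the comparison is secondary only in section 2. Section 3 states it as a purpose and sizes two groups, and section 5.4 names outcomes for it. That is correct. The fault is an inconsistency between section 2 and the design, not the absence of a planned comparison.

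Two stronger readings are tempting, and the documents support neither.
- A reader might infer seven between-group tests from the seven outcomes in section 2 and compute an error rate for seven. That objective contains no comparison, and section 5.4 does not list OS, TFS and PFS as separate tests.
- A reader might infer that outcomes were chosen after the results were seen. The records existed, but nothing shows whether outcomes had been analysed by group when the plan was written.

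It is also fair to say that the error rates depend on assumptions. The documents give no correlations, event rates or test count, and treating GFR, blood loss and complications as the outcomes most open to chance findings is a judgement.

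**Conclusion.** The point holds as a defect of specification that should be corrected. That no outcome or time is primary, that section 2 does not match sections 3 and 5.4, and that no hierarchy or adjustment accompanies the blanket 5% rule can all be read directly from the text and need no assumption.

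The size is illustrative: roughly 10–14% for three between-group tests and 17–21% with three GFR periods, against the 5% that one primary test would carry. These figures assume no true differences, full 5% error on each counted test and the correlations stated, and they shift by a few points if those change. They are neither an upper limit, since section 5.3 and the open lists would raise them, nor an estimate of what this study will produce.

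**What to change.** - **Section 2.** Align the main objective with the two-group comparison in sections 3 and 5.4. Name one primary outcome at one fixed postoperative time. The between-group difference in percentage change in GFR is an example, as GFR is listed first; the choice is the sponsor's. State the date on which it was named and whether outcomes had by then been analysed by group. Give the remaining outcomes as a closed secondary list, remove both uses of 'etc.', and keep the modified ABC score objective as secondary.
- **Section 5.4.** Replace the open 'such as' wording with a reference to that list.
- **Sections 5.3 and 6.3.** Suggested text: *Only the primary outcome is tested as confirmatory, at two-sided 0.05. All other comparisons, including the score-group analyses in 5.3, are reported as estimates with 95% confidence intervals and labelled exploratory. A non-significant result is not read as no difference.*
- **If outcomes had already been analysed by group,** label all comparisons exploratory, including the one that would have been primary.

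The cost is wording in sections 2, 5.3, 5.4 and 6.3, with no new patients or data. The downside is that fewer results can be called confirmatory, and a primary outcome named after the records exist is weaker than true pre-specification.

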## **3. Study content and design**

This study aims to evaluate the effectiveness and safety of the surgery by using renal cancer patients who met the inclusion criteria. Summarizing the preoperative, perioperative, and postoperative data, and evaluating the operative time, intraoperative bleeding, postoperative hospitalization days, postoperative complication rate, postoperative short-term, intermediate, and long-term renal function indexes, overall survival, tumor-free survival, progression-free survival and postoperative renal cancer recurrence rate of the patients.

Statistical software is used to describe the characteristics of patient data. T-test, rank sum test, multi-factor regression, and cox regression are used to investigate the effects of each factor on the treatment outcome and prognosis of patients undergoing zero-ischemic renal enucleation, to describe whether there are differences in the safety and efficacy of zero ischemic renal enucleation compared with traditional

partial nephrectomy for the treatment of stage T1 renal carcinoma.

This study used a retrospective research trial design to include 73 patients who underwent zero-ischemic enucleation and 73 patients who underwent traditional partial nephrectomy from 2014 to 2022, for a total of 146 patients. The formula for calculating the sample size is as follows.

$$n = [z_{\alpha}\sqrt{2\bar{p}\bar{q}} + z_{\beta}\sqrt{p_0q_0 + p_1q_1}]^2 p / (p_1 - p_0)^2$$

Figure 1. Estimated sample size calculation

note:  $Z_{\alpha}$ 、 $Z_{\beta}$  are the quartiles under standard normal distribution.

$p_1$ : Expected morbidity in the exposed group.

$p_0$ : Expected incidence in the control group.

$q_1$ :  $q_1 = 1 - p_1$ .

$q_0$ :  $q_0 = 1 - p_0$ .

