## 4. Study population

### 4.1 Inclusion criteria

1. The age is between 18 and 80 years old.
2. Stage T1a or T1b according to the 8th edition of the AJCC TNM staging of kidney cancer, 2017.
3. The patients who underwent PN or TE between 2014 and 2022.

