### 4.2 Exclusion criteria

1. With severe active infection or serious cardiac, hepatic, renal and hematopoietic diseases; and other physical conditions that make them unsuitable for the test in question (as judged by the investigator).
2. The patient has no measurable or evaluable lesions.
3. The tumor is close to the collecting system, touching the renal artery or renal vein, and other anatomical conditions that are not

suitable for nephrectomy.

4. History of organ transplantation or need for long-term adrenocorticotrophic hormone therapy; hypothyroidism, adrenal or pituitary function that cannot be controlled with hormone replacement therapy alone, type I diabetes, psoriasis or vitiligo requiring systemic treatment, etc.

5. The presence of active infection requiring systemic therapy. The presence of human immunodeficiency virus (HIV) infection (known to be HIV antibody positive). The presence of active HBV or HCV infection (HBsAg positive individuals, or HBcAb positive but HBsAg negative individuals who require additional DNA quantification and whose results do not exceed the upper limit of normal values in the study center laboratory can participate in this study. Previous HCV infected patients with negative HCV RNA test results during the screening period can participate in this study).

6. Have a history of kidney surgery or any inflammatory kidney surgery, have kidney cancer associated with the urinary collection system, and have other kidney diseases (including kidney stones and glomerulonephritis).

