## **7. Informed consent**

Previous case information is used for this study and a waiver of informed consent is requested.

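### Section 5.2 equalises the two arms by screening records whose perioperative outcomes already exist, and the readable text gives no rule for which eligible cases stay

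*Combined protocol and SAP*

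**What the plan says.** Section 3 states the design: "This study used a retrospective research trial design". The study will "include 73 patients who underwent zero-ischemic enucleation and 73 patients who underwent traditional partial nephrectomy from 2014 to 2022", 146 in all, and the number is set beside a two-proportion sample size formula. Section 7 confirms the data source: "Previous case information is used for this study and a waiver of informed consent is requested".

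Three places bear on who enters:

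- Section 4.1 sets the window: "The patients who underwent PN or TE between 2014 and 2022". Section 4.2, exclusion 1, lists certain diseases and then leaves room for "other physical conditions that make them unsuitable for the test in question (as judged by the investigator").
- Section 5.1 screens on these criteria and splits patients by operation.
- Section 5.2 adds a second step. The groups are corrected for baseline and "screened so that there is no statistical difference in the number of patients", and likewise in sex, age, tumor anatomy, renal function and other preoperative conditions, with p > 0.05 on a t-test or rank sum test as the criterion.

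On the available cases, section 1 reports: "In the last 3 years, our team has performed nearly 100 cases of zero-ischemic renal tumor enucleation". No count of partial nephrectomies (PN) is given anywhere.

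**The concern.** The protocol is dated February 2023 and the operations run to 2022. Blood loss, complications, margins and early renal function are therefore already in the charts when cases are picked. In that setting, the rule that decides which eligible cases are kept is what protects the comparison from bias.

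Section 5.2 makes equal numbers and non-significant baseline differences the target but does not say how to reach it. Someone following it exactly may try one subset and then another, and may prefer the one whose outcomes look better without breaking any written rule. Adjustment for age, anatomy or renal function does not repair this, because selection on outcome can operate among patients with identical preoperative values. Every between-group comparison in section 5.4 would be affected.

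**Working it through.** **1. Can 73 be derived?** The section 3 formula is, in its usual form (setting aside a trailing symbol that may come from reading the PDF):

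n = [z_α √(2 p̄ q̄) + z_β √(p0 q0 + p1 q1)]² / (p1 − p0)²

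No values are given for p0, p1 or power, so 73 cannot be reproduced. It is compatible with some inputs. For 15% vs 35%, two-sided 5% and 80% power: [1.96 × √0.375 + 0.8416 × √0.355]² / 0.04 = (1.200 + 0.501)² / 0.04 ≈ 72.4, rounded up to 73. Other inputs do not fit: 10% vs 20% needs 199 per arm. So the formula does not show whether 73 was a target or simply the number of cases available.

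**2. Does section 5.2 remove eligible patients?** Patient number is not something a t-test or rank sum test compares between two groups, so the natural reading is that arm sizes are to be made equal. If the eligible pools are N1 and N0 and N1 ≠ N0, at least |N1 − N0| eligible patients must go. If N1 = N0 but baseline differs at p ≤ 0.05, some must still go. Only pools that are equal and already balanced avoid this.

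**3. Does p > 0.05 identify a single set?** No. With 73 per arm, a continuous variable passes whenever the standardised difference is below about 1.96 × √(2/73) = 1.96 × 0.1655 = 0.32. Any subset within that band, in either direction, meets the rule. Where the pool is appreciably larger than 73, many subsets will.

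**4. How far could outcomes move?** Pool sizes and event counts below are assumptions. For E events in a pool of N, an unrestricted choice of 73 can hold from max(0, E − (N − 73)) to min(73, E) events.

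| Assumed eligible pool | Assumed events | Left out | Expected in a random 73 | Possible range |
|---|---|---|---|---|
| 73 | any | 0 | all | no freedom |
| 80 | 16 | 7 | 14.6 (20%) | 9 to 16 (12.3% to 21.9%) |
| 100 | 20 | 27 | 14.6 (20%) | 0 to 20 (0% to 27.4%) |

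In the last row, a random 73 would hold 5 or fewer events with probability about 5 × 10⁻⁷ (hypergeometric), yet free choice allows it. Against an arm with 15/73 events, 5/73 gives Fisher p = 0.028, so selection alone could make two arms with the same underlying rate look different. In the 80-case row the lowest possible count is 9. Even 8/73 against 15/73 gives p = 0.17, so selection in that arm alone would not reach significance. These are outer bounds: they ignore the baseline requirement, which restricts the choice somewhat.

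**5. Is there a protective rule elsewhere?** Sections 3 to 6 contain no requirement for consecutive or all eligible cases, random sampling, a matching algorithm, blinding of the selector to outcome, or a count of eligible cases left out. The data-management text in section 6.3 protects personal identity; it does not separate selection from outcomes. Figure 2, the flow diagram, could not be seen.

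**The case against.** The best defence is that nothing improper need lie behind the numbers.

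- The section 1 count of zero-ischemia cases covers renal tumors before any eligibility criterion. Restriction to T1 cancer and ages 18 to 80, with the long exclusion list, could plausibly reduce it to 73. **This stands.** Equally, that count covers only three years, so the pool across the whole window could be larger. The documents settle neither.
- A reader might infer from the equal arms that cases were discarded at will on both sides. **The documents do not support that.** Choosing one comparable control for each of 73 eligible enucleations gives the same result.
- A reader might also infer a large PN pool from the nine calendar years. **That is a time window, not a count.** The team's PN volume is never stated, so a precision gain from using more controls cannot be quantified.
- Section 5.2 names only preoperative variables and may be meant as matching. That is fair as to intent. But matching needs a named method, a closed list of variables and an order of operations, and none is given.
- Figure 2 might contain selection steps. It might, so the point is limited to the written text, and sections 5.1 and 5.2 would still need to state the rule.
- The judgement clause in exclusion 1 is confined to physical conditions and is not itself a fault. What matters is whether it is applied before or after outcomes are seen.

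**Conclusion.** The point holds as a gap in the selection rule. In a retrospective study with perioperative outcomes already recorded, section 5.2 directs that numbers and baseline be equalised by screening, and the readable text leaves open which eligible patients are dropped. The plan thus permits selection that depends on outcome, and later adjustment would not correct it.

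A reader might go further and conclude that favourable cases were picked. Nothing in the documents shows this; 73 may be every eligible zero-ischemia case.

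The size is unknown because neither eligible pool is stated. In the zero-ischemia arm it runs from no freedom (73 eligible) to about 27 of 100 cases left out (27%) if all of roughly 100 were eligible; a larger pool over 2014 to 2022 would widen it. The event-rate ranges above rest on assumed pools and a 20% event rate, and bound what the rule allows rather than predict what occurred. The missing p0, p1 and power are a separate defect on which this point does not depend.

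**What to change.** In sections 3 and 5.2:

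1. Replace the fixed 73 and 73 with all consecutive eligible zero-ischemia and PN cases in the window, taken from the dated operating list. If 73 is already every eligible zero-ischemia case, say so.
2. If there are too many PN charts to abstract, take a random sample of eligible PN cases, or controls matched by an algorithm on named preoperative variables. Write the algorithm down in advance.
3. Decide eligibility, including the investigator-judgement exclusion, from recorded preoperative facts before outcome data are linked.
4. Drop screening to p > 0.05. Handle baseline by adjustment, weighting or the fixed matching in step 2.
5. Report the numbers screened, eligible and excluded, with reasons, for each arm.

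The cost is some extra chart abstraction from existing records, with no recruitment. The amount cannot be estimated because the PN volume is not given; the random-sample or matched option limits it. Any precision gain depends on the same unknown and is not claimed here.
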